## 9. Balance Assessment

**Action report links:**

Optum: <https://bwh-dope.aetion.com/projects/details/1484/results/64541/result/0>

Marketscan: <https://bwh-dope.aetion.com/projects/details/1481/results/64542/result/0>

Medicare: <https://bwh-dope.aetion.com/projects/details/1483/results/64543/result/0>

Date conducted: 1/19/2021

After review of initial feasibility and power analyses, complete creation of the remaining covariates from Section 6.2. Again, using the dummy outcome of a 90-day gap in database enrollment, complete a 1:1 PS-matched analysis. The PS should include the complete list of covariates.

- Provide plot of PS distributions stratified by treatment group.

Note- Please refer to **Appendix B**.

- Report covariate balance after matching.

Note- For Table 1, please refer to **Appendix B**.

- Report reasons for censoring by treatment group.

|  | Overall | Referent | Exposure |
|--|---------|----------|----------|
|--|---------|----------|----------|

|                                                                                                                               |                |                |                |
|-------------------------------------------------------------------------------------------------------------------------------|----------------|----------------|----------------|
| Dummy outcome                                                                                                                 | 67 (0.94%)     | 25 (0.70%)     | 42 (1.18%)     |
| Death                                                                                                                         | 103 (1.44%)    | 49 (1.37%)     | 54 (1.51%)     |
| Start of an additional exposure                                                                                               | 232 (3.25%)    | 175 (4.90%)    | 57 (1.60%)     |
| End of index exposure                                                                                                         | 4,701 (65.84%) | 2,202 (61.68%) | 2,499 (70.00%) |
| Specified date reached                                                                                                        | 857 (12.00%)   | 424 (11.88%)   | 433 (12.13%)   |
| End of patient enrollment                                                                                                     | 425 (5.95%)    | 198 (5.55%)    | 227 (6.36%)    |

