| ...Missing; n (%)                                                           | 1,450 (98.5%)   | 2,746 (98.7%)   | -0.02 | 2,464 (100.0%)        | 3,868 (99.8%)     | 0.06    | N/A         | N/A         | 3,914 (99.4%)    | 6,614 (99.4%)   | 0.00        |         |  |
| Lab result number- BUN (mg/dl) mean v2                                      | 290             | 642             |       | 18                    | 49                |         | N/A         | N/A         | 308              | 691             |             |         |  |
| ...mean (sd)                                                                | 14.97 (5.67)    | 14.75 (4.93)    | 0.04  | 11,126.96 (35,122.84) | 14.95 (5.16)      | 0.45    | N/A         | N/A         | 664.37 (8292.09) | 14.76 (4.95)    | 0.11        |         |  |
| ...Missing; n (%)                                                           | 1,182 (80.3%)   | 2,141 (76.9%)   | 0.08  | 2,446 (99.3%)         | 3,825 (98.7%)     | 0.06    | N/A         | N/A         | 3,628 (92.2%)    | 5,966 (89.6%)   | 0.09        |         |  |
| Lab result number- Creatinine (mg/dl) mean (only 0.1 to 15 included) v3     | 292             | 674             |       | 18                    | 52                |         | N/A         | N/A         | 310              | 726             |             |         |  |
| ...mean (sd)                                                                | 0.91 (0.29)     | 0.92 (0.23)     | -0.04 | 1.05 (0.31)           | 0.95 (0.19)       | 0.39    | N/A         | N/A         | 0.92 (0.29)      | 0.92 (0.23)     | 0.00        |         |  |
| ...Missing; n (%)                                                           | 1,180 (80.2%)   | 2,109 (75.8%)   | 0.11  | 2,446 (99.3%)         | 3,822 (98.7%)     | 0.06    | N/A         | N/A         | 3,626 (92.1%)    | 5,931 (89.1%)   | 0.10        |         |  |
| Lab result number- HDL level (mg/dl) mean (only <5000 included) v2          | 164             | 376             |       | 11                    | 37                |         | N/A         | N/A         | 175              | 413             |             |         |  |
| ...mean (sd)                                                                | 54.89 (18.99)   | 49.89 (16.20)   | 0.28  | 48.00 (11.92)         | 42.95 (12.24)     | 0.42    | N/A         | N/A         | 54.46 (18.71)    | 49.27 (15.91)   | 0.30        |         |  |

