| ...Missing; n (%)                                                           | 485 (99.0%)    | 480 (98.0%)       | 0.08  | 1,381 (100.0%)        | 1,378 (99.8%)       | 0.06    | N/A         | N/A         | 1,866 (99.7%)      | 1,858 (99.3%)  | 0.06             |         |
| Lab result number- BUN (mg/dl) mean v2                                      | 107            | 107               | 11    | 21                    |                     |         | N/A         | N/A         | 118                | 128            |                  |         |
| ...mean (sd)                                                                | 14.59 (4.94)   | 14.77 (5.11)      | -0.04 | 18,197.88 (44,223.54) | 14.28 (4.67)        | 0.58    | N/A         | N/A         | 1709.64 (1304.81)  | 14.69 (5.06)   | 0.18             |         |
| ...Missing; n (%)                                                           | 383 (78.2%)    | 383 (78.2%)       | 0.00  | 1,370 (99.2%)         | 1,360 (98.5%)       | 0.07    | N/A         | N/A         | 1,753 (93.7%)      | 1,743 (93.2%)  | 0.02             |         |
| Lab result number- Creatinine (mg/dl) mean (only 0.1 to 15 included) v3     | 109            | 115               | 9     | 23                    |                     |         | N/A         | N/A         | 118                | 138            |                  |         |
| ...mean (sd)                                                                | 0.89 (0.22)    | 0.90 (0.23)       | -0.04 | 1.02 (0.21)           | 0.94 (0.18)         | 0.41    | N/A         | N/A         | 0.90 (0.22)        | 0.91 (0.22)    | -0.05            |         |
| ...Missing; n (%)                                                           | 381 (77.8%)    | 375 (76.5%)       | 0.03  | 1,372 (99.3%)         | 1,358 (98.3%)       | 0.09    | N/A         | N/A         | 1,753 (93.7%)      | 1,733 (92.6%)  | 0.04             |         |
| Lab result number- HDL level (mg/dl) mean (only <5000 included) v2          | 58             | 66                | 4     | 20                    |                     |         | N/A         | N/A         | 62                 | 86             |                  |         |
| ...mean (sd)                                                                | 53.28 (16.01)  | 51.19 (15.56)     | 0.13  | 43.75 (16.07)         | 45.90 (14.63)       | -0.14   | N/A         | N/A         | 52.67 (16.15)      | 49.96 (15.45)  | 0.17             |         |

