| ...Missing; n (%)                                                           | 430 (87.8%)    | 422 (86.1%)       | 0.05  | 1,377 (99.7%)         | 1,362 (98.6%)       | 0.12    | N/A         | N/A         | 1,807 (96.6%)      | 1,784 (95.4%)  | 0.06             |         |
| Lab result number- Hemoglobin mean (only >0 included)                       | 83             | 97                | 6     | 17                    |                     |         | N/A         | N/A         | 89                 | 114            |                  |         |
| ...mean (sd)                                                                | 13.73 (1.94)   | 13.73 (1.83)      | 0.00  | 40,008.30 (62,283.25) | 14.48 (1.45)        | 0.91    | N/A         | N/A         | 2709.99 (15017.83) | 13.84 (1.79)   | 0.25             |         |
| ...Missing; n (%)                                                           | 407 (83.1%)    | 393 (80.2%)       | 0.07  | 1,375 (99.6%)         | 1,364 (98.8%)       | 0.09    | N/A         | N/A         | 1,782 (95.2%)      | 1,757 (93.9%)  | 0.06             |         |
| Lab result number- Serum sodium mean (only >90 and <190 included)           | 103            | 102               | 9     | 22                    |                     |         | N/A         | N/A         | 112                | 124            |                  |         |
| ...mean (sd)                                                                | 140.36 (2.80)  | 140.11 (2.59)     | 0.09  | 137.64 (4.57)         | 140.09 (1.89)       | -0.70   | N/A         | N/A         | 140.14 (2.98)      | 140.11 (2.49)  | 0.01             |         |
| ...Missing; n (%)                                                           | 387 (79.0%)    | 388 (79.2%)       | 0.00  | 1,372 (99.3%)         | 1,359 (98.4%)       | 0.08    | N/A         | N/A         | 1,759 (94.0%)      | 1,747 (93.4%)  | 0.02             |         |
| Lab result number- Albumin mean (only >0 and <=10 included)                 | 95             | 100               | 8     | 16                    |                     |         | N/A         | N/A         | 103                | 116            |                  |         |
| ...mean (sd)                                                                | 4.08 (0.41)    | 4.08 (0.40)       | 0.00  | 4.00 (0.32)           | 4.16 (0.48)         | -0.39   | N/A         | N/A         | 4.07 (0.41)        | 4.09 (0.41)    | -0.05            |         |

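### Appendix B: the BUN and hemoglobin lab rules have no upper limit, so impossible values drive their MarketScan and pooled standardized differences in the balance table

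*Combined protocol and SAP*

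**What the plan says.** Appendix B lists 13 numeric lab results, and the row labels state the range applied.

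- Ten have an upper limit. Creatinine, for example, is "Lab result number- Creatinine (mg/dl) mean (only 0.1 to 15 included) v3" and albumin is "Lab result number- Albumin mean (only >0 and <=10 included". HbA1c, sodium, glucose and potassium are also bounded on both sides, and the four lipids are capped at 5,000.
- Three have none: BNP, BUN ("Lab result number- BUN (mg/dl) mean v2") and hemoglobin ("Lab result number- Hemoglobin mean (only >0 included").

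For MarketScan warfarin patients, the BUN mean and SD are "11,126.96 (35,122.84" in the unmatched table and "18,197.88 (44,223.54" in the matched table. The matched hemoglobin cell reads "40,008.30 (62,283.25". The matched apixaban means beside them are 14.28 and 14.48.

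Section 9 asks for covariate balance after matching. Section 10 then stops the analyses until the investigators, FDA and advisory board members have reviewed balance and power.

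**The concern.** A mean BUN of 18,198 mg/dl or a mean hemoglobin of 40,008 cannot be real. The Optum warfarin means in the same matched rows are 14.59 and 13.73, so the fault lies in the MarketScan values that the rules let through. It is not a fault of text extraction, because it appears in both the unmatched and matched tables and the pooled means recompute from it.

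A standardized difference built on such values says nothing about how alike the arms are. The hemoglobin figure of 0.91 is the largest among the matched MarketScan lab rows. The error also passes into the pooled columns, which summarize all three databases. These figures go to a review that must finish before the comparative analyses start.

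**Working it through.** **Inputs (Appendix B, MarketScan).** The number of patients with a value is the group size minus the Missing row.

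| Row | Warfarin n | Warfarin mean (SD) | Apixaban mean (SD) | Printed difference |
|---|---|---|---|---|
| BUN, unmatched | 2,464 − 2,446 = 18 | 11,126.96 (35,122.84) | 14.95 (5.16) | 0.45 |
| BUN, matched | 1,381 − 1,370 = 11 | 18,197.88 (44,223.54) | 14.28 (4.67) | 0.58 |
| Hemoglobin, unmatched | 2,464 − 2,451 = 13 | 18,472.91 (45,243.58) | 14.22 (1.44) | 0.58 |
| Hemoglobin, matched | 1,381 − 1,375 = 6 | 40,008.30 (62,283.25) | 14.48 (1.45) | 0.91 |

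**Step 1: reproduce the printed differences.** Standardized difference = (m1 − m2) / √[(s1² + s2²)/2].

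- BUN, matched: (18,197.88 − 14.28) / √[(44,223.54² + 4.67²)/2] = 0.581.
- Hemoglobin, matched: (40,008.30 − 14.48) / √[(62,283.25² + 1.45²)/2] = 0.908.
- Unmatched: 0.447 and 0.577.

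All four agree with the table.

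**Step 2: reproduce the pooled means** (Optum plus MarketScan; Medicare has no lab values).

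- BUN: (107 × 14.59 + 11 × 18,197.88) / 118 = 1,709.64.
- Hemoglobin: (83 × 13.73 + 6 × 40,008.30) / 89 = 2,709.99.

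Both agree. The pooled hemoglobin difference recomputes to 0.25. The pooled BUN difference of 0.18 needs an SD of about 13,041. The extracted text shows 1304.81, probably a lost digit, and this is not counted as an error.

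**Step 3: how many outliers?** Suppose the ordinary values sit near a base c (15 for BUN, 13.5 for hemoglobin).

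- One outlier would give matched SDs of about 60,306 and 97,967, against 44,223.54 and 62,283.25 printed. One is ruled out.
- For two outliers, let A = n·mean − (n − 2)c and B = (n − 1)SD² + n·mean² − (n − 2)c². The two values are [A ± √(2B − A²)] / 2.

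| Row | Solution |
|---|---|
| BUN, unmatched | 139,966 and 60,079 |
| BUN, matched | 139,969 and 60,073 |
| Hemoglobin, unmatched | 130,004 and 109,996 |
| Hemoglobin, matched | 130,023 and 109,973 |

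Two tables with different n return nearly the same pairs. As a check against round values, the matched BUN sum of squares is 23,200,006,103 ± 6,424 (rounding), and 140,000² + 60,000² = 23,200,000,000. For hemoglobin it is 29,000,000,566 ± 5,515, and 130,000² + 110,000² = 29,000,000,000. Both fit.

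**Step 4: matched figures without those values**, assuming they are exactly the round pairs.

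- BUN sum: 11 × 18,197.88 − 200,000 = 176.68, so the mean of the other 9 is 19.63. Pooled: (107 × 14.59 + 176.68) / 116 = 14.98, against 14.69 for apixaban.
- Hemoglobin sum: 6 × 40,008.30 − 240,000 = 49.80, so the mean of the other 4 is 12.45. Pooled: (83 × 13.73 + 49.80) / 87 = 13.67, against 13.84 for apixaban.
- If the values are instead divided by 10,000, the MarketScan means are (176.68 + 20)/11 = 17.88 and (49.80 + 24)/6 = 12.30.

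The corrected MarketScan warfarin SD cannot be recovered from rounded figures, so a range is assumed.

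| Lab | Assumed SD | Difference if dropped | Difference if rescaled |
|---|---|---|---|
| BUN | 4.3 to 10 | 1.19 to 0.69 | 0.80 to 0.46 |
| Hemoglobin | 0.7 to 3 | −1.78 to −0.86 | −1.91 to −0.93 |

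With pooled warfarin SDs near the Optum values (about 5 and 1.9), the pooled differences after dropping become about 0.06 and −0.09.

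**The case against.** The strongest reply is that this is a cosmetic fault in a lab panel that informs nobody. Much of that stands. Only 11 of 1,381 (0.8%) and 6 of 1,381 (0.4%) matched MarketScan warfarin patients have a value. Labs that do have limits also show large differences in that column: triglycerides 0.80, sodium −0.70, total cholesterol 0.67, HbA1c 0.52. Each of these rests on 3 to 9 warfarin patients. The protocol states no threshold for a standardized difference, so no prespecified decision turns on these rows, and a careful reader would see that the means are impossible. The reply does not reach the pooled columns, where the printed 0.18 and 0.25 suggest an imbalance that largely disappears on correction.

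Four stronger readings are tempting and are not supported.

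- **That the outliers damaged the propensity score.** Section 9 says "The PS should include the complete list of covariates", and Section 6.2 points to Table 1 for that list, so a reader might infer that raw lab results were in the model. Nothing shows this. BUN appears in the part of the table marked for the propensity score only as whether a test was ordered (36 vs 42 in matched MarketScan, difference −0.02). Raw BUN and hemoglobin are 98.5% to 99.6% missing in matched MarketScan and absent in Medicare. A complete-case model on them could not have produced 1,381 pairs.
- **That a filter restores balance in MarketScan.** Step 4 shows that it does not.
- **That two mis-scaled records per lab are a fact.** The fit is very close and one record is excluded, but three or more unequal records cannot be strictly excluded. A 10,000-fold scale error is only a possible cause.
- **That the creatinine limit demonstrably removed such records,** because 20 unmatched MarketScan warfarin patients have a creatinine value and 18 are used. Optum creatinine also falls (297 to 292 and 679 to 674), as does MarketScan LDL under its loose cap (13 to 11 and 37 to 34). The documents do not say why.

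**Conclusion.** The point holds as a minor correction to the balance table. The BUN and hemoglobin rules, as labelled and applied, admit impossible values. The MarketScan differences (0.45 and 0.58 unmatched, 0.58 and 0.91 matched) and the matched pooled ones (0.18 and 0.25) do not measure the real contrast between arms, and the pooled warfarin means are wrong. These statements rest on printed figures alone.

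The corrected sizes rest on assumptions: two outlying results per lab at the round values, and the SD ranges shown. On that footing the pooled warfarin means become about 15.0 and 13.7. The MarketScan BUN difference stays at roughly 0.5 to 1.2, and hemoglobin reverses to roughly −0.9 to −1.9. With so few patients these are uninformative either way. No effect on matching or on the hazard ratio is claimed. BNP also lacks a stated limit, but its means are not evidently impossible.

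**What to change.** Give BUN and hemoglobin a plausible two-sided range, stated in the row label as for the other labs. Any upper limit below about 60,000 for BUN and 110,000 for hemoglobin would remove the inferred values, so the correction does not depend on the exact limit. Recompute both rows, with their MarketScan and pooled standardized differences, in the unmatched and matched tables before the balance review. Note beside them how few MarketScan patients have a value.

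State in Section 9 whether raw lab results enter the propensity score. Refit and rematch MarketScan only if they do.

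The cost is two filter edits and a re-run of Table 1. If the inference is right, two results per lab are lost.

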# Appendix B

|                                                                                            |               |               |           |               |               |           |               |               |           |               |               |         |
|--------------------------------------------------------------------------------------------|---------------|---------------|-----------|---------------|---------------|-----------|---------------|---------------|-----------|---------------|---------------|---------|
| Non-Frailty; n (%)                                                                         | 206 (42.0%)   | 210 (42.9%)   | -0.02     | 581 (42.1%)   | 583 (42.2%)   | 0.00      | 57 (3.4%)     | 47 (2.8%)     | 0.03      | 844 (23.6%)   | 840 (23.5%)   | 0.00    |
| Frailty Score (mean): Empirical Version
365 days, v2                                    |               |               |           |               |               |           |               |               |           |               |               |         |
| ...mean (sd)                                                                               | 0.18 (0.06)   | 0.18 (0.06)   | 0.00      | 0.15 (0.05)   | 0.15 (0.05)   | 0.00      | 0.10 (0.07)   | 0.10 (0.08)   | 0.00      | 0.13 (0.06)   | 0.13 (0.07)   | 0.00    |
| Healthcare Utilization                                                                     |               |               |           |               |               |           |               |               |           |               |               |         |
| Any hospitalization; n (%)                                                                 | 438 (89.4%)   | 453 (92.4%)   | -0.10     | 1,379 (99.9%) | 1,380 (99.9%) | 0.00      | 1,564 (92.1%) | 1,555 (91.5%) | 0.02      | 3,381 (94.7%) | 3,388 (94.9%) | -0.01   |
| Any hospitalization within prior 30 days; n (%)                                            | 374 (76.3%)   | 364 (74.3%)   | 0.05      | 1,287 (93.2%) | 1,302 (94.3%) | -0.05     | 1,204 (70.9%) | 1,229 (72.3%) | -0.03     | 2865 (80.3%)  | 2895 (81.1%)  | -0.02   |
| Any hospitalization during prior 31-180 days; n (%)                                        | 101 (20.6%)   | 121 (24.7%)   | -0.10     | 185 (13.4%)   | 166 (12.0%)   | 0.04      | 565 (33.3%)   | 546 (32.1%)   | 0.03      | 851 (23.8%)   | 833 (23.3%)   | 0.01    |
| Internal medicine/family medicine visits; n (%)                                            | 427 (87.1%)   | 427 (87.1%)   | 0.00      | 1,079 (78.1%) | 1,090 (78.9%) | -0.02     | 1,606 (94.5%) | 1,626 (95.7%) | -0.06     | 3112 (87.2%)  | 3143 (88.0%)  | -0.02   |
| Internal medicine/family medicine visits (30 days prior); n (%)                            | 361 (73.7%)   | 360 (73.5%)   | 0.00      | 753 (54.5%)   | 821 (59.4%)   | -0.10     | 1,399 (82.3%) | 1,402 (82.5%) | -0.01     | 2513 (70.4%)  | 2583 (72.4%)  | -0.04   |
| Internal medicine/family medicine visits (31 to 180 days prior); n (%)                     | 294 (60.0%)   | 294 (60.0%)   | 0.00      | 855 (61.9%)   | 817 (59.2%)   | 0.06      | 1,184 (69.7%) | 1,140 (67.1%) | 0.06      | 2333 (65.4%)  | 2251 (63.1%)  | 0.05    |
| Cardiologist visit; n (%)                                                                  | 352 (71.8%)   | 365 (74.5%)   | -0.06     | 393 (28.5%)   | 375 (27.2%)   | 0.03      | 1,203 (70.8%) | 1,213 (71.4%) | -0.01     | 1948 (54.6%)  | 1953 (54.7%)  | 0.00    |
| Number of Cardiologist visits (30 days prior); n (%)                                       | 297 (60.6%)   | 308 (62.9%)   | -0.05     | 271 (19.6%)   | 270 (19.6%)   | 0.00      | 880 (51.8%)   | 902 (53.1%)   | -0.03     | 1448 (40.6%)  | 1480 (41.5%)  | -0.02   |
| Number of Cardiologist visits (31 to 180 days prior); n (%)                                | 111 (22.7%)   | 123 (25.1%)   | -0.06     | 173 (12.5%)   | 165 (11.9%)   | 0.02      | 558 (32.8%)   | 563 (33.1%)   | -0.01     | 842 (23.6%)   | 851 (23.8%)   | 0.00    |
| Electrocardiogram v2; n (%)                                                                | 401 (81.8%)   | 415 (84.7%)   | -0.08     | 694 (50.3%)   | 691 (50.0%)   | 0.01      | 1,449 (85.3%) | 1,442 (84.9%) | 0.01      | 2544 (71.3%)  | 2548 (71.4%)  | 0.00    |
| Use of glucose test strips; n (%)                                                          | ** (1.2%)     | ** (1.4%)     | -0.02     | 19 (1.4%)     | ** (0.8%)     | 0.06      | 31 (1.8%)     | 29 (1.7%)     | 0.01      | #VALUE!       | #VALUE!       | #VALUE! |
| Dialysis; n (%)                                                                            | 0 (0.0%)      | ** (0.2%)     | -0.06     | 0 (0.0%)      | ** (0.1%)     | -0.04     | ** (0.1%)     | ** (0.1%)     | 0.00      | #VALUE!       | #VALUE!       | #VALUE! |
| number of different/distinct medication prescriptions                                      |               |               |           |               |               |           |               |               |           |               |               |         |
| ...mean (sd)                                                                               | 7.88 (5.51)   | 8.00 (5.83)   | -0.02     | 7.89 (4.81)   | 8.01 (5.76)   | -0.02     | 9.33 (6.22)   | 9.31 (6.22)   | 0.00      | 8.57 (5.62)   | 8.63 (5.99)   | -0.01   |
| Number of Hospitalizations                                                                 |               |               |           |               |               |           |               |               |           |               |               |         |
| ...mean (sd)                                                                               | 1.11 (0.72)   | 1.08 (0.56)   | 0.05      | 1.17 (0.48)   | 1.16 (0.49)   | 0.02      | 1.30 (0.93)   | 1.29 (0.93)   | 0.01      | 1.22 (0.76)   | 1.21 (0.74)   | 0.01    |
| Number of hospital days                                                                    |               |               |           |               |               |           |               |               |           |               |               |         |
| ...mean (sd)                                                                               | 5.44 (4.46)   | 5.11 (7.06)   | 0.06      | 5.43 (4.09)   | 5.28 (6.21)   | 0.03      | 5.85 (5.04)   | 5.73 (7.43)   | 0.02      | 5.63 (4.61)   | 5.47 (6.93)   | 0.03    |
| Number of Emergency Department (ED) visits v3                                              |               |               |           |               |               |           |               |               |           |               |               |         |
| ...mean (sd)                                                                               | 1.79 (2.37)   | 1.82 (2.21)   | -0.01     | 3.20 (5.17)   | 3.17 (4.44)   | 0.01      | 2.70 (7.14)   | 2.73 (4.23)   | -0.01     | 2.77 (5.95)   | 2.78 (4.10)   | 0.00    |
| Number of Office visits                                                                    |               |               |           |               |               |           |               |               |           |               |               |         |
| ...mean (sd)                                                                               | 5.01 (4.71)   | 5.03 (4.44)   | 0.00      | 4.72 (4.41)   | 4.77 (5.34)   | -0.01     | 10.37 (13.98) | 10.07 (11.65) | 0.02      | 7.45 (10.18)  | 7.33 (8.85)   | 0.01    |
| Number of internal medicine/family medicine visits                                         |               |               |           |               |               |           |               |               |           |               |               |         |
| ...mean (sd)                                                                               | 10.16 (13.90) | 9.39 (12.98)  | 0.06      | 5.30 (7.34)   | 5.51 (8.85)   | -0.03     | 12.46 (13.83) | 11.04 (12.11) | 0.11      | 9.37 (11.76)  | 8.67 (11.10)  | 0.06    |
| Number of Cardiologist visits                                                              |               |               |           |               |               |           |               |               |           |               |               |         |
| ...mean (sd)                                                                               | 2.58 (3.80)   | 2.62 (3.94)   | -0.01     | 0.71 (1.95)   | 0.70 (1.90)   | 0.01      | 2.81 (4.52)   | 2.89 (4.25)   | -0.02     | 1.97 (3.63)   | 2.01 (3.48)   | -0.01   |
| Number of electrocardiograms received v2                                                   |               |               |           |               |               |           |               |               |           |               |               |         |
| ...mean (sd)                                                                               | 1.98 (2.00)   | 2.10 (2.02)   | -0.06     | 0.90 (1.31)   | 0.92 (1.37)   | -0.01     | 2.31 (2.51)   | 2.35 (2.54)   | -0.02     | 1.72 (2.05)   | 1.76 (2.09)   | -0.02   |
| Number of HbA1c tests ordered                                                              |               |               |           |               |               |           |               |               |           |               |               |         |
| ...mean (sd)                                                                               | 0.28 (0.63)   | 0.29 (0.64)   | -0.02     | 0.22 (0.51)   | 0.22 (0.55)   | 0.00      | 0.29 (0.62)   | 0.29 (0.60)   | 0.00      | 0.26 (0.58)   | 0.26 (0.59)   | 0.00    |
| Number of glucose tests ordered                                                            |               |               |           |               |               |           |               |               |           |               |               |         |
| ...mean (sd)                                                                               | 0.14 (0.62)   | 0.17 (0.73)   | -0.04     | 0.13 (1.17)   | 0.13 (0.60)   | 0.00      | 0.15 (0.60)   | 0.17 (0.60)   | -0.03     | 0.14 (0.87)   | 0.15 (0.62)   | -0.01   |
| Number of lipid tests ordered                                                              |               |               |           |               |               |           |               |               |           |               |               |         |
| ...mean (sd)                                                                               | 0.37 (0.62)   | 0.39 (0.74)   | -0.03     | 0.38 (0.72)   | 0.36 (0.66)   | 0.03      | 0.36 (0.65)   | 0.37 (0.64)   | -0.02     | 0.37 (0.67)   | 0.37 (0.66)   | 0.00    |
| Total N distinct ICD9/ICD10 diagnoses at the 3rd digit level Copy                          |               |               |           |               |               |           |               |               |           |               |               |         |
| ...mean (sd)                                                                               | 12.13 (12.97) | 12.28 (12.70) | -0.01     | 10.37 (10.13) | 10.29 (10.87) | 0.01      | 17.46 (15.46) | 17.28 (15.89) | 0.01      | 13.99 (13.29) | 13.89 (13.71) | 0.01    |
| For PS                                                                                     |               |               |           |               |               |           |               |               |           |               |               |         |
| Hemorrhagic stroke+Other cerebrovascular disease+Cerebrovascular procedure (for PS); n (%) |               |               |           |               |               |           |               |               |           |               |               |         |
| ...mean (sd)                                                                               | ** (1.4%)     | ** (1.2%)     | 0.02      | 11 (0.8%)     | 11 (0.8%)     | 0.00      | 31 (1.8%)     | 31 (1.8%)     | 0.00      | #VALUE!       | #VALUE!       | #VALUE! |
| Major trauma potentially causing prolonged hospitalization (for PS); n (%)                 |               |               |           |               |               |           |               |               |           |               |               |         |
| ...mean (sd)                                                                               | 16 (3.3%)     | #DIV/0!       | 31 (2.2%) | 33 (2.4%)     | #DIV/0!       | 92 (5.4%) | 92 (5.4%)     | #DIV/0!       | 31 (2.2%) | 33 (2.4%)     | -0.01         |         |
| Occurrence of creatinine tests ordered (for PS); n (%)                                     |               |               |           |               |               |           |               |               |           |               |               |         |
| ...mean (sd)                                                                               | 30 (6.1%)     | 30 (6.1%)     | 0.00      | 80 (5.8%)     | 72 (5.2%)     | 0.03      | 129 (7.6%)    | 151 (8.9%)    | -0.05     | 239 (6.7%)    | 253 (7.1%)    | -0.02   |
| Occurrence of BUN tests ordered (for PS); n (%)                                            |               |               |           |               |               |           |               |               |           |               |               |         |
| ...mean (sd)                                                                               | 13 (2.7%)     | 15 (3.1%)     | -0.02     | 36 (2.6%)     | 42 (3.0%)     | -0.02     | 63 (3.7%)     | 81 (4.8%)     | -0.05     | 112 (3.1%)    | 138 (3.9%)    | -0.04   |
| Occurrence of chronic renal insufficiency w/o CKD (for PS); n (%)                          |               |               |           |               |               |           |               |               |           |               |               |         |
| ...mean (sd)                                                                               | ** (1.0%)     | ** (0.6%)     | 0.04      | ** (0.5%)     | ** (0.5%)     | 0.00      | 18 (1.1%)     | 26 (1.5%)     | -0.04     | #VALUE!       | #VALUE!       | #VALUE! |
| Chronic kidney disease Stage 1-2 (for PS); n (%)                                           |               |               |           |               |               |           |               |               |           |               |               |         |
| ...mean (sd)                                                                               | ** (1.4%)     | ** (1.6%)     | -0.02     | ** (0.7%)     | ** (0.4%)     | 0.04      | 28 (1.6%)     | 27 (1.6%)     | 0.00      | #VALUE!       | #VALUE!       | #VALUE! |
| Chronic kidney disease Stage 3-6 (for PS); n (%)                                           |               |               |           |               |               |           |               |               |           |               |               |         |
| ...mean (sd)                                                                               | 16 (3.3%)     | 15 (3.1%)     | 0.01      | 34 (2.5%)     | 23 (1.7%)     | 0.06      | 79 (4.6%)     | 92 (5.4%)     | -0.04     | 129 (3.6%)    | 130 (3.6%)    | 0.00    |
| Acute kidney injury; n (%)                                                                 |               |               |           |               |               |           |               |               |           |               |               |         |
| ...mean (sd)                                                                               | 38 (7.8%)     | 43 (8.8%)     | #DIV/0!   | 99 (7.2%)     | 98 (7.1%)     | #DIV/0!   | 168 (9.9%)    | 184 (10.8%)   | #DIV/0!   | 99 (7.2%)     | 98 (7.1%)     | 0.00    |
| Bladder stones+Kidney stones (for PS); n (%)                                               |               |               |           |               |               |           |               |               |           |               |               |         |
| ...mean (sd)                                                                               | 21 (4.3%)     | 19 (3.9%)     | 0.02      | 39 (2.8%)     | 49 (3.5%)     | -0.04     | 62 (3.6%)     | 64 (3.8%)     | -0.01     | 122 (3.4%)    | 132 (3.7%)    | -0.02   |
| Alcohol abuse or dependence+Drug abuse or dependence (for PS); n (%)                       |               |               |           |               |               |           |               |               |           |               |               |         |
| ...mean (sd)                                                                               | 33 (6.7%)     | 36 (7.3%)     | -0.02     | 46 (3.3%)     | 49 (3.5%)     | -0.01     | 156 (9.2%)    | 145 (8.5%)    | 0.02      | 235 (6.6%)    | 230 (6.4%)    | 0.01    |
| Other atherosclerosis+Cardiac conduction disorders+Other CVD (for PS) v2 Copy; n (%)       |               |               |           |               |               |           |               |               |           |               |               |         |
| ...mean (sd)                                                                               | 155 (31.6%)   | 149 (30.4%)   | 0.03      | 394 (28.5%)   | 402 (29.1%)   | -0.01     | 500 (29.4%)   | 539 (31.7%)   | -0.05     | 1049 (29.4%)  | 1090 (30.5%)  | -0.02   |

